Title: Dietary Management of Gestational Diabetes Mellitus

NCT ID not yet assigned

Document date: 2021.11.23

Study protocol

Participants

The target population was selected from 48 patients with gestational diabetes mellitus attending the obstetrics outpatient clinic of the Affiliated Hospital of XXX. The study objects were selected by non synchronous control, for example, patients who visited the hospital in the first week were included in the control group, and patients who visited the hospital in the second week were included in the experimental group until saturation.

Intervention

The intervention group

The intervention group received a 12-week dietary management intervention based on the nudge strategy. The MINDSPACE framework was used, which has nine intervention categories. Face-to-face intervention and telephone follow-up were used to provide targeted dietary management.

The control group

During the intervention, patients in the control group received routine obstetric health education and instruction under contamination, but no additional information on dietary management based on nudge strategies.

Statistical analysis plan

Data collection

From October 21, 2022 to December 31, 2022 (prospective), data was collected. At the time of enrollment, demographic information about the study participants was gathered. Pre-intervention, 1-month post-intervention and 3-months post-intervention, patients' glucose level indicators (FPG, 2hPG) and pregnancy outcomes were collected. The study subjects had no knowledge of group assignments.

Statistical analysis

All statistical analyses were carried out using SPSS, version 26.0 (SPSS Inc., Chicago, IL, USA). Continuous variables with normal distributions were expressed as $x \pm s$ and compared between groups using the independent samples t-test; continuous variables with non-normal distributions were expressed as M (Q1, Q3) and compared

between groups using the Wilcoxon rank sum test; categorical variables were expressed as cases (%) and compared between groups using χ^2 test and categorical variables were described as percentages and compared using chi-square test. Metrics that are repeated the time effect, the main effect of the intervention, and the interaction effect of both FBG and 2hPG before, 1 month after, and 3 months after the intervention were all compared in the two groups using ANOVA. $P < 0.05$ with two tailed significance was considered statistically significant.

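### Pregnancy outcomes are tied to the fixed glucose visits and a 72-day collection window, with no collection at delivery, so women undelivered by then may have no outcome

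*Combined protocol and SAP*

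**What the plan says.** The Data collection section of the statistical analysis plan covers both endpoints in one sentence, which lists a pre-intervention time, a 1-month time and then "3-months post-intervention, patients' glucose level indicators (FPG, 2hPG) and pregnancy outcomes were collected". The document mentions no delivery visit, no review of birth records, and no rule for a woman still pregnant at the last visit. The pregnancy outcomes are not named.

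The same section fixes the dates: "From October 21, 2022 to December 31, 2022 (prospective), data was collected".

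Under Intervention, the programme is given a length: "The intervention group received a 12-week dietary management intervention based on the nudge strategy". The Statistical analysis section times the glucose measurements as "before, 1 month after, and 3 months after the intervention were all compared in the two groups using ANOVA". Neither place says whether the months run from the start or the end of the 12 weeks.

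For categorical outcomes the analysis is that "categorical variables were expressed as cases (%) and compared between groups using χ^2 test". Participants are described as "selected from 48 patients with gestational diabetes mellitus attending the obstetrics outpatient clinic". No gestational age at entry is given.

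**The concern.** Outcomes of pregnancy exist only once a woman has delivered. None can be recorded before the intervention, and few if any 1 month after entry. If the last collection is about 3 months from entry, it takes place while some women may still be pregnant. Whether a woman contributes an outcome then depends on how early she delivers. Timing of birth is itself a likely pregnancy outcome and is related to others, so the sample would be selected on the quantity being measured.

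The planned t-test, rank sum and chi-square comparisons do nothing to correct this. At stake are the absolute rates reported for each group, the number of women contributing, and, if the groups differ in gestation at entry, the comparison between them.

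**Working it through.** The plan states no delivery rate, event rate or sample size calculation, so there is no figure of its own to reproduce.

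**Step 1. Dates (from the documents).** 21 October to 31 December 2022 is 72 days counting both ends, or 72/7 = 10.3 weeks. The intervention is 12 × 7 = 84 days. Three months is about 91 days, or 13 weeks. For a woman entering on the first day:
- the 12-week course ends 84 days later, on 13 January 2023;
- a 3-month visit counted from the start falls on about 21 January 2023;
- a 3-month visit counted from the end falls about 12 + 13 = 25 weeks after entry, in April 2023.

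All three are after 31 December 2022.

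**Step 2. Model (assumptions, not in the documents).** Gestation at delivery is normal with mean 39 and SD 1.5 weeks. Entry gestation g is uniform over a stated range. Preterm means before 37 weeks.
- True preterm rate = Φ((37 − 39)/1.5) = Φ(−1.33) = 9.1%.
- Share delivered w weeks after entry at gestation g: c(g) = Φ((g + w − 39)/1.5).
- Capture = average of c(g) over the entry range.
- Preterm share among captured = average of min(9.1%, c(g)) divided by capture.

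**Step 3. Visit 13 weeks from the start.** At single entry gestations:
- 24 weeks: Φ(−1.33) = 9%
- 26 weeks: Φ(0) = 50%
- 28 weeks: Φ(1.33) = 91%
- 30 weeks: Φ(2.67) = 99.6%

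For entry at 24 weeks or later, g + 13 is at least 37, so the preterm share reduces to 9.12% divided by capture.

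| Entry (weeks) | Captured | Preterm among captured |
|---|---|---|
| 24-28 | 50% | 9.12/50.0 = 18.2% |
| 24-32 | 74% | 9.12/74.2 = 12.3% |
| 26-30 | 85% | 9.12/85.1 = 10.7% |
| 28-32 | 98% | 9.12/98.4 = 9.3% |

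Varying the delivery distribution (means 38.5 to 39.3, SDs 1.5 to 1.7) gives 9-16% captured for entry at 24 weeks, 43-63% at 26 weeks and 84-95% at 28 weeks.

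**Step 4. Collection closes on 31 December 2022.** Take the most favourable case, every woman entering on day 1, so w = 10.3. For entry at 24-28 weeks capture is 8%, and 59% of those births are preterm. For entry at 28-32 weeks capture is 75%, with 12% preterm. Later entry lowers capture.

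**Step 5. Visits counted from the end.** With w = 25, a woman entering at 24 weeks would be at 24 + 25 = 49 weeks. Capture is effectively 100% and the preterm share equals the true 9.1%. The 3-month glucose values are then taken after birth.

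**Step 6. Between groups.** Suppose there is no treatment effect and mean entry differs by one week, with entry uniform within 2 weeks either side of 25.5 in one group and 26.5 in the other. With w = 13, capture is 40% against 60%, and preterm among captured is 22% against 15%. If the entry distributions are the same, both rates are inflated equally when there is no treatment effect, and no false difference arises.

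**The case against.** The strongest reply is that the sentence is loosely written and means glucose three times and pregnancy outcomes once. Two facts favour it: a pre-intervention pregnancy outcome is impossible, and the repeated-measures ANOVA is specified only for FBG and 2hPG. This may well be the intention. But the plan does not say so, and even on this reading it gives no collection at delivery and keeps the 31 December 2022 close.

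A second reply is that, read literally, both timing phrases place the visits after the 12 weeks have ended. Step 5 shows that the selection then vanishes. That stands, which is why the point is conditional. The cost is that the 3-month glucose measurements become largely postpartum, at a date far outside the stated window.

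Third, the size rests on assumptions. That also stands: the bias runs from a doubling of the preterm rate to almost nothing, depending on an entry gestation that the plan does not report. Preterm birth is used here only as an example, because the plan names no pregnancy outcome and designates none as primary.

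A reader might infer that half of the 48 women will have no outcome, or that the comparison between groups is necessarily biased. The documents support neither. The first needs entry at 24-28 weeks and a start-based visit, and the wording leaves open whether 48 is the number enrolled or the pool they came from. The second needs the groups to differ in gestation at entry. Non-randomised allocation by week of visit does not rule that out, but nothing in the text shows it.

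**Conclusion.** The point holds conditionally. As written, the plan ties pregnancy outcomes to the glucose time points, gives no delivery time point, and closes collection before any 3-month visit could take place under either origin. If visits count from the start of the intervention, or if collection ends on the stated date, undelivered women have no outcome and early births are over-represented.

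Under the assumed delivery distribution, capture at a 13-week visit lies between 50% and 98% for the entry ranges considered. With the 72-day close and entry on day 1, it lies between about 8% and 75%. Bias in the comparison between groups is possible but not established. Counting from the end removes this selection and moves the difficulty to the 3-month glucose measurement.

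This is a cheap improvement. It does not show that the planned comparison must fail.

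**What to change.** - Separate pregnancy outcomes from the glucose visits. Name them, and collect them once, at delivery, for every enrolled woman from the obstetric record, or by telephone if she delivers elsewhere. Use all enrolled women as the denominator.
- Keep pregnancy-outcome follow-up open until the last enrolled woman has delivered, and change the 31 December 2022 close to match.
- Remove pregnancy outcomes from the pre-intervention and 1-month collections.
- State whether the 1- and 3-month glucose visits count from the start or the end of the 12 weeks, and reconcile the collection dates with that choice.

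Apart from loss to follow-up, every enrolled woman then has an outcome and the selection on timing of birth is gone. The cost is a few sentences in the Data collection section and use of routine delivery records. The small downside is that the pregnancy-outcome report waits for the last delivery.

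### Women are assigned by clinic week but no planned test includes week, so the between-group tests are anti-conservative if outcomes correlate within enrolment week

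*Combined protocol and SAP*

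**What the plan says.** The Participants section of the study protocol describes a non-concurrent comparison: "The study objects were selected by non synchronous control". The illustration that follows is the only assignment rule given. For the control arm, "patients who visited the hospital in the first week were included in the control group"; for the other arm, "patients who visited the hospital in the second week were included in the experimental group until saturation". No randomisation is described. The number of weeks is not stated, nor whether the weeks alternate or each arm is one block. On numbers, the section says only that "The target population was selected from 48 patients with gestational diabetes mellitus".

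The Statistical analysis section of the SAP sets out the tests. Normally distributed variables are "compared between groups using the independent samples t-test"; other continuous variables go to a rank-sum test and categorical variables to chi-square. The repeated glucose measures "were all compared in the two groups using ANOVA", with time, intervention and interaction effects. Tests are two-sided at 0.05. Enrolment week appears in none of them as a cluster, random effect or covariate, and no ICC or design effect is given.

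**The concern.** The week decides the arm, and everyone seen in that week gets the same arm. The planned tests nevertheless take the woman as the independent unit. Their error term is built from differences between women within an arm, so it does not properly carry any variation between weeks, although the comparison of arms is itself a comparison of weeks.

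Women enrolled in the same week might share staff, teaching or laboratory conditions. The documents do not say that they do; these are possible sources of correlation. If some correlation exists, the between-group p-values and any confidence intervals are too optimistic. This is a matter of variance and is separate from selection or a calendar trend: it would remain with unselected enrolment and no trend. At stake is whether a p-value just under 0.05 means what it appears to mean in a study of about 48 women.

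**Working it through.** **Plan's own figure.** There is none to reproduce. The documents give no power, effect size, SD, ICC or number of weeks.

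**Inputs from the documents.** Assignment by week (Participants); two-sided 0.05 and tests without a week term (Statistical analysis); 48 women (Participants).

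**Assumptions.** 24 women per arm (25 in the five-week case, as 5 weeks of 5), equal week sizes, normal outcomes, and an ICC of 0.01 to 0.05.

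**Formulas.** With m women per week, the design effect is DE = 1 + (m − 1) × ICC. The true standard error is about √DE times the one that the t-test uses. The actual two-sided error is about 2 × [1 − Φ(1.96/√DE)].

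**t-test.** DE and error are given for ICC 0.01 and then 0.05.

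| Weeks per arm | m | DE | Error by formula | Error by simulation |
|---|---|---|---|---|
| 1 | 24 | 1.23; 2.15 | 7.7%; 18.1% | 7.7%; 18.9% |
| 2 | 12 | 1.11; 1.55 | 6.3%; 11.5% | 6.1%; 11.6% |
| 4 | 6 | 1.05; 1.25 | 5.6%; 8.0% | 5.6%; 8.1% |
| 5 | 5 | 1.04; 1.20 | 5.5%; 7.4% | 5.4%; 7.5% |

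Example, one week per arm at ICC 0.05: DE = 1 + 23 × 0.05 = 2.15; √2.15 = 1.466; 1.96/1.466 = 1.337; error 18.1%. At ICC 0, DE is 1 and the error is 5% for any number of weeks. The rank-sum and chi-square tests were not simulated; they ignore week in the same way, so the direction is the same.

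**Repeated-measures ANOVA, main effect of intervention.** Assume total variance 1, half stable between women and half within, with a stable week component of 0.05. A woman's mean over three visits then has variance 0.5 + 0.5/3 = 0.667, so the ICC of that mean is 0.05/0.667 = 0.075.
- One week per arm: DE = 1 + 23 × 0.075 = 2.725, error about 24% (simulated 25%).
- Two weeks per arm: DE = 1.825, error about 15% (simulated 15%).
- Four weeks per arm: DE = 1.375, error about 9% (simulated 10%).

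**Repeated-measures ANOVA, time-by-group interaction.** This is a contrast within each woman, so a stable week effect cancels; simulated error was 4.6% to 5.2%. If instead 5% of the within-woman variance is shared by week at each visit, the simulated error is 26%, 16% and 9% with one, two and four weeks per arm.

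**Analysis on week means.** Degrees of freedom are the total number of weeks minus 2: 0 with one week per arm (no standard error exists), 2 with two (critical t 4.30), 6 with four (2.45) and 8 with five. Simulated error stayed at about 5% wherever the test could be computed. With five weeks per arm and an assumed 0.8 SD effect, power is 0.68 at ICC 0.01 and 0.62 at ICC 0.05. The individual-level t-test appears to have 0.79 and 0.77, but does not hold its 5%.

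**The case against.** A reader might infer that the standard errors are definitely too small, in every test, by the amounts seen with one week per arm. The documents do not support that, for three reasons.

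- **Inflation needs a positive within-week correlation, and none is documented.** Post-intervention glucose is measured one and three months on, not in the enrolment week, and the intervention is described as targeted, which may weaken any shared week effect. At ICC 0.01 with four weeks per arm, the standard error is only about 2.5% too small (√1.05 = 1.025). This stands, so the conclusion has to be conditional.
- **The interaction is exempt when week effects are stable.** It is the plan's test of differential change in glucose, so the exception matters. It does not cover the main effect of intervention or the t, rank-sum and chi-square comparisons.
- **One week per arm is only one reading.** The rule is introduced as an illustration ("The study objects were selected by non synchronous control, for example") and can also be read as weeks alternating until the arms are full. If each arm really is one week, the difficulty is confounding, and a random week effect cannot be separated from arm. The largest error figures therefore belong to a case that no variance correction repairs.

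It can also be objected that a random-intercept model is a weak remedy here. With four or five weeks per arm and an ICC of 0.01 to 0.05, simulation of its balanced-design equivalent put the week variance at zero in about 39-52% of trials, with an overall error of about 3.4-4.1%. That stands too, and is why week means should lead.

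What survives is the mismatch. Leaving week out amounts to assuming an ICC of exactly zero, without saying so, under a rule that assigns by week.

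**Conclusion.** The point holds in conditional form. If outcomes correlate within enrolment week, the planned between-group comparisons are anti-conservative, by an amount that the documents do not allow one to compute. The sizes shown rest on the assumed ICC of 0.01 to 0.05, equal weeks and 24 to 25 women per arm. On those assumptions the effect on the t-test is modest with five weeks per arm and serious with one or two. The number and order of weeks matter most, and the plan states neither. It should be corrected, with medium confidence as to its practical size.

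**What to change.** 1. Record enrolment week for every woman.
2. State in the protocol the number and order of recruitment weeks, with arms alternating over several weeks (at least four or five per arm) and never one block each.
3. Test the between-group effects on week means. Give a model with a random week intercept and small-sample degrees of freedom (for example SPSS MIXED with Satterthwaite) as a supporting analysis.
4. If only one or two weeks per arm are achieved, report that week and arm cannot be separated and do not present the p-value as evidence of an intervention effect. With one week per arm the separation is impossible. With two, the week-mean test has 2 degrees of freedom and is too weak to be useful.

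**Cost.** The data field and the SAP wording are cheap. Intervals widen and power falls, to about 0.62-0.68 in the five-week case above. The week schedule is a real change to the design. Five alternating weeks per arm take 70 days, while the stated data-collection window (21 October to 31 December 2022) is 11 + 30 + 31 = 72 days, about 10.3 weeks, and must also hold follow-up. The schedule and the window have to be reconciled.

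### Groups are formed by week of attendance, yet any continuous pregnancy outcome gets only an unadjusted two-group test, although pre-intervention glucose and demographics are collected

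*Combined protocol and SAP*

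**What the plan says.** **Allocation (Study protocol, Participants).** "The study objects were selected by non synchronous control". The example given is that "patients who visited the hospital in the first week were included in the control group", with second-week attenders going to the experimental group. The number given is 48 ("The target population was selected from 48 patients with gestational diabetes mellitus"). The wording leaves open whether 48 is the pool or the enrolled number, and no group ratio is stated.

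**Baseline data (Statistical analysis plan, Data collection).** "At the time of enrollment, demographic information about the study participants was gathered", but the variables are not listed. Before the intervention and at 1 and 3 months, "patients' glucose level indicators (FPG, 2hPG) and pregnancy outcomes were collected". The pregnancy outcomes are not named, and their type is not given.

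**Analysis (Statistical analysis plan, Statistical analysis).** Normal continuous variables are "compared between groups using the independent samples t-test", non-normal ones by the Wilcoxon rank sum test, and categorical ones by chi-square. An ANOVA with time, group and interaction effects covers FBG and 2hPG only. The section names no covariate, regression, stratification or matching. It does not say which test applies to pregnancy outcomes; the two-group tests are simply the only listed methods left for them.

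**The concern.** Women who attend in different weeks may differ systematically in glycaemia, age or referral route. A baseline factor that predicts the outcome and differs between the groups appears in an unadjusted comparison as if it were an intervention effect. The glucose ANOVA at least includes the pre-intervention value as one of its time points. A continuous pregnancy outcome has no pre-intervention value of its own, and the plan brings no baseline information into its comparison.

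A baseline significance test would not be a safeguard. With 24 per group it misses a true 0.5 SD difference about 60% of the time, so covariates should not be chosen by baseline P values either.

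**Working it through.** The documents give no effect size, SD, event rate or power, so there is no figure of the plan's own to reproduce. The calculations below illustrate size only.

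**Inputs**
- From the documents: 48 patients; two-sided alpha 0.05.
- Assumed: 1:1 split, so n = 24 per group.
- Assumed: within-group correlation r between baseline covariate and outcome of 0.3 to 0.5, with 0.1 as a weak case.
- Assumed: baseline difference D of 0.3 or 0.5 SD.

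**1. Standard error of the unadjusted difference, in outcome SD units.** sqrt(2/24) = 0.289.

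**2. Shift in the unadjusted difference = r × D.**
- D = 0.3: 0.3 × 0.3 = 0.09 and 0.5 × 0.3 = 0.15 SD.
- D = 0.5: 0.3 × 0.5 = 0.15 and 0.5 × 0.5 = 0.25 SD.

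**3. False-positive rate when the difference is systematic** (the weekly populations truly differ by D). The rate is P(|Z + shift/0.289| > 1.96).

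| D | r = 0.1 | r = 0.3 | r = 0.5 |
|---|---|---|---|
| 0.3 SD | 5.1% | 6.1% | 8.1% |
| 0.5 SD | 5.3% | 8.1% | 13.9% |

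**4. False-positive rate conditional on a realised chance imbalance of D.** The difference now varies with standard error 0.289 × sqrt(1 − r²), but is still judged against 1.96 × 0.289 = 0.566.
- D = 0.3: 5.1% (r = 0.3) and 5.0% (r = 0.5).
- D = 0.5, r = 0.3: standard error 0.275; (0.566 − 0.15)/0.275 = 1.51; both tails give 7.0%.
- D = 0.5, r = 0.5: standard error 0.250; (0.566 − 0.25)/0.250 = 1.26; both tails give 10.4%.

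**5. How often chance alone produces such imbalances on one covariate.** 2(1 − Φ(0.3/0.289)) = 30% for 0.3 SD or more. 2(1 − Φ(0.5/0.289)) = 8% for 0.5 SD or more.

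**6. Power of a baseline t-test.** For a true 0.5 SD difference with 46 degrees of freedom it is 39.6%, so 60.4% are missed.

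**7. Precision, net of two covariates, groups balanced on average.** The variance ratio is (1 − r²) × 45/43, taking r as the joint correlation of both covariates with the outcome. The equivalent gain in sample size is 1/ratio − 1.
- r = 0.1: 0.99 × 1.0465 = 1.036, a loss of about 3%.
- r = 0.3: 0.91 × 1.0465 = 0.952, a gain of 5%.
- r = 0.5: 0.75 × 1.0465 = 0.785, a gain of 27%.

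**8. Precision when one covariate differs systematically by 0.5 SD.** Removing that difference adds (0.25/43)/(2/24) = 0.070 to the factor, giving 1.0465 + 0.070 = 1.116. The ratios become 0.91 × 1.116 = 1.016 (r = 0.3) and 0.75 × 1.116 = 0.837 (r = 0.5). The bias protection and the full precision gain therefore do not arrive together: at r = 0.3 the gain is gone, and at r = 0.5 it falls to about 19%.

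**The case against.** **The target may be empty.** The plan names no pregnancy outcome, and the t-test sentence is a general rule for continuous variables. If the outcomes are all categorical, the regression proposed here changes nothing. This stands, and the point is limited to continuous outcomes for that reason.

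**The correlation is assumed.** This also stands. At r = 0.1 adjustment costs a little precision, and even at r = 0.3 the net gain is only about 5%. Precision alone would make this an optional suggestion.

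**Chance imbalance is not bias.** A reader might infer that with 24 per group, frequent imbalance makes the unadjusted test invalid under any allocation. It does not. Under randomisation the test keeps its 5% rate overall, and even conditional on a 0.3 SD imbalance the rate stays near 5%. What the documents support is the narrower argument from non-random weekly allocation.

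**The error rates can be overstated.** Dividing the shift by the adjusted standard error would give about 9% (0.3 SD) and 17% (0.5 SD) at r = 0.5. The planned test uses the full outcome SD, so those figures do not apply to it.

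**Replacing the Wilcoxon test with linear regression removes a safeguard for non-normal outcomes at this size.** That is fair. The fix therefore keeps the planned test as support and asks for robust standard errors or a residual check.

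**Conclusion.** The omission is real and worth correcting, but does not by itself invalidate the trial. Groups are non-randomised, relevant baseline data are collected, and no stated analysis uses them for pregnancy outcomes. The main reason to adjust is validity. A systematic 0.5 SD baseline difference would shift an unadjusted result by 0.15 to 0.25 SD and give about 8% to 14% false positives (6% to 8% at 0.3 SD). The corresponding rates conditional on a realised chance imbalance are 7% to 10% and about 5%. Precision is a secondary benefit: 5% to 27% more women if the groups are balanced on average, and less if they are not.

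These sizes rest on 24 per group, r of 0.3 to 0.5 and an assumed imbalance, none of which the documents give. That continuous pregnancy outcomes exist, and that they fall to these tests, is inferred by elimination.

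Two stronger readings are not supported. The documents contain no baseline results, so they do not show that the groups in fact differ. Nor would adjustment repair the allocation, since it cannot remove unmeasured or calendar-week confounding. Confidence is medium.

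**What to change.** In the SAP, before analysis:

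1. Name the pregnancy outcomes and their type, and assign each an analysis.
2. For each continuous pregnancy outcome, make the main comparison a linear regression on group, pre-intervention FPG and maternal age (if recorded). Fix the covariates in advance, and do not select them by baseline P values.
3. Report the adjusted mean difference with a 95% CI, using robust standard errors or a stated residual check.
4. Keep the unadjusted t-test or Wilcoxon test as a supporting analysis.
5. Keep rare binary outcomes unadjusted, with exact tests; 48 women cannot support adjusted models for them.
6. State that adjustment does not remove unmeasured or calendar-week confounding.

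The cost is SAP wording, a few lines in the SPSS already specified, and 2 of 46 degrees of freedom under the assumed 48 analysed. No new data are needed if maternal age is among the demographics.

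### The planned main effect of the intervention counts the pre-intervention glucose value as an outcome, so it is diluted to two thirds and absorbs any baseline difference, and no other test is named as decisive

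*Combined protocol and SAP*

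**What the plan says.** The Statistical analysis section describes a two-group repeated-measures ANOVA. Apart from an effect of time, it examines "the main effect of the intervention, and the interaction effect of both FBG and 2hPG before, 1 month after, and 3 months after" treatment; FBG here is the fasting measure called FPG in the Data collection section. Two-sided P < 0.05 applies to every test. No baseline covariate, primary measure, primary time point or deciding effect is named. The t-test and Wilcoxon test are listed for continuous variables in general, without an outcome or a visit.

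Under Participants, groups are formed by calendar week. The rule given for controls is "patients who visited the hospital in the first week were included in the control group". The corresponding rule for the intervention arm is "patients who visited the hospital in the second week were included in the experimental group until saturation".

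The Data collection section sets the glucose measurements at "Pre-intervention, 1-month post-intervention and 3-months post-intervention" and gives the window: "From October 21, 2022 to December 31, 2022 (prospective), data was collected". Under Intervention: "The intervention group received a 12-week dietary management intervention based on the nudge strategy".

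**The concern.** The intervention cannot change a value measured before it starts. Averaging that value into the outcome does two things:

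- It pulls a real effect towards zero, so the effect may be missed.
- It puts any pre-existing group difference into the quantity labelled as the intervention effect, so a significant result can arise with no treatment effect.

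The second matters more here than in a randomised trial, because week-of-visit allocation allows systematic differences between groups. Since the three ANOVA effects have equal standing, the main effect can be reported as the treatment result.

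**Working it through.** The plan gives no power calculation, SD, correlation or effect size, so there is no stated figure to reproduce.

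**Inputs from the documents:** three time levels, two groups, 48 patients, two-sided 0.05, allocation by week.

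**Assumed, not in the documents:** n = 24 per group, SD = 1 at each visit, equal correlation r between visits (0.3, 0.5, 0.7, 0.8), complete data.

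**1. What the main effect estimates.** Let b be the group difference at baseline, and D1 and D3 the differences at 1 and 3 months.

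- Main effect = (b + D1 + D3)/3.
- With b = 0 it is (D1 + D3)/3, which is 2/3 of the average follow-up effect (D1 + D3)/2. For D1 = D3 = 0.8 it is 0.533.
- With no treatment effect and a lasting difference, D1 = D3 = b and the main effect is b, carried in full.
- If the difference fades to r times its size, the main effect is b(1 + 2r)/3.

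This step needs none of the assumed figures, except r in the last line.

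**2. False positives with no treatment effect.** The main effect has variance (1 + 2r)/3 × 2/n. At r = 0.5 this is 0.667 × 2/24, an SE of 0.236. A lasting b of 0.5 SD then gives 0.5/0.236 = 2.12 standard errors; the noncentral t (46 df) gives 55%.

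| Main effect rejects (%) | r = 0.3 | 0.5 | 0.7 | 0.8 |
|---|---|---|---|---|
| Lasting 0.5 SD | 64 | 55 | 47 | 45 |
| Lasting 0.3 SD | 29 | 24 | 21 | 19 |
| Lasting 0.2 SD | 15 | 13 | 12 | 11 |
| 0.5 SD, fading to r times its size | 24 | 28 | 33 | 35 |

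The other tests at 0.5 SD (simulated, 40,000 trials per cell):

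| Rejects (%) | r = 0.3 | 0.5 | 0.7 | 0.8 |
|---|---|---|---|---|
| Interaction, lasting | 5 | 5 | 5 | 5 |
| Adjusted average, lasting | 33 | 21 | 13 | 10 |
| Adjusted 3-month, lasting | 22 | 16 | 11 | 9 |
| Interaction, fading | 16.5 | 13.0 | 9.5 | 8.1 |
| Both adjusted contrasts, fading | 5 | 5 | 5 | 5 |

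**3. Cost of the dilution.** The baseline-adjusted average of both follow-ups estimates (D1 + D3)/2 − r·b, with variance (1 − r)(1 + 2r)/2 × 2/n. With b = 0, the number of patients the main effect needs, relative to this contrast, for equal power is

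[2/((1 − r)(1 + 2r))] / [(4/9) × 3/(1 + 2r)] = 1.5/(1 − r).

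This is 2.1, 3.0, 5.0 and 7.5 at the four values of r. If correlation decays with time it is 1.8, 2.3, 3.4 and 4.9. For non-negative correlations it is never below 1.25.

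**4. Power with equal starting groups** (per cent, in the order r = 0.3/0.5/0.7/0.8; simulated, and matching noncentral t and F calculations to within about a point):

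| Effect at 1 / 3 months (SD) | Main effect | Interaction | Adjusted average | Adjusted 3-month |
|---|---|---|---|---|
| 0.6 / 0.6 | 46/39/33/31 | 41/55/78/93 | 77/81/92/98 | 56/64/80/92 |
| 0.3 / 0.6 | 29/24/21/20 | 32/44/65/84 | 52/57/72/84 | 56/64/81/92 |
| 0 / 0.6 | 15/13/12/11 | 42/55/78/93 | 27/30/39/50 | 56/64/80/92 |
| 0.6 / 0.3 | 29/24/21/19 | 32/43/66/83 | 53/57/71/84 | 19/22/29/39 |
| 0.6 / 0 | 15/13/12/11 | 42/55/78/92 | 27/29/39/50 | 5/5/5/5 |

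The adjusted average beats the main effect in all 20 cells. It does not always beat the interaction, and loses clearly when the effect is present at one visit only.

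**5. Dates.** October 21 to December 31, 2022 is 71 days, and 12 weeks is 84 days. A patient measured on the first day reaches 12 weeks on January 13, 2023, 84 − 71 = 13 days after collection ends. If the window opens with the first control week, the first second-week patient starts on October 28 and reaches 12 weeks 84 − 64 = 20 days after it ends.

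**The case against.** The plan never says that the main effect decides. It also lists the group-by-time interaction, the usual treatment test in a pre/post ANOVA, which is undiluted and holds 5% under a lasting difference. The generic t-test could be applied at 3 months, with about 53% power for a 0.6 SD effect whatever the value of r. The high false-positive rates need a systematic baseline gap that the documents do not show; with chance imbalance alone the main effect holds 5% over repeated samples. A smaller change would let group-by-time, or a one-degree-of-freedom change contrast, decide.

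Much of this is true, and it narrows the point. An informative test is planned, but nothing separates it from a misleading one of equal standing. The interaction has 2 degrees of freedom, gives no single estimate, and exceeds 5% if a baseline difference fades. The t-test is tied to no outcome or visit.

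A change contrast would be a defensible choice, since under a lasting difference it is the unbiased one. Its price is precision: its variance is 1.5(1 − r) × 2/n, so the adjusted average has (1 + 2r)/3 of that variance, or 0.53, 0.67, 0.80 and 0.87 at the four values of r. Neither method is safe in every case with non-random groups, so both should be reported, with the decisive one named beforehand.

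**Conclusion.** The concern holds. The two-thirds dilution and the carry-over of a baseline difference follow from the planned model and need no assumed figures. The error rates and power values are conditional on 24 per group, equal SDs, the stated correlations and complete data; the false-positive rates also need the assumed baseline gap. The advantage claimed for adjustment is over the three-level main effect only. Adjustment does not cure non-random allocation, and any 3-month result depends on data that the stated window does not cover. This should be fixed before analysis: as written, a group difference that existed before treatment could be reported as the effect of the intervention.

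**What to change.** 1. State that no treatment conclusion is drawn from the three-level main effect.
2. Name one deciding contrast on one measure, FPG or 2hPG: the baseline-adjusted group difference with 95% CI from SPSS MIXED. The 1- and 3-month values are the outcomes. Fixed effects are group, time, group-by-time, the same measure's baseline and baseline-by-time, with unstructured covariance. Say whether the contrast is averaged over both follow-ups (the like-for-like replacement for the main effect) or taken at one visit (suited to an effect expected mainly then). The other measure and contrasts are secondary.
3. Report the group-by-time (change from baseline) result as a sensitivity analysis that does not alter the deciding test.
4. State the limit: the adjusted contrast is biased if a group difference persists, and the change-based result if it fades. The documents do not show which applies.
5. Before choosing a time point, reconcile the data collection dates with the 12-week intervention and the 3-month measurement.

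The cost is SAP wording, a different SPSS procedure and two added model terms, using values already collected and no new patients. There are two trade-offs. A result on the measure not chosen no longer decides. If the effect occurs at one follow-up only, the averaged contrast has less power than the interaction.
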